- **Chart Stimulated Recall (CSR).** An established technique for examining clinician decision-making and clinical processes beyond what can be determined from chart review or self-report alone. A trained research team member will review the clinician's caseload with them for the past clinic week and ask them brief questions (no more than 5 minutes) related to the clinician's suicide-related practices (e.g., "Did you conduct a screen for suicide risk? How did you screen for risk? If risk was present, was a full CSSRS/SPI administered?). This will be administered at Time 1 and 3-4. No identifiable patient information is collected during the CSR and the study staff will not ever view the chart directly. Clinicians are instructed to refrain from sharing any identifiable patient details during the CSR administration.
 - o This measure was previously reviewed and approved by the IRB.
- **Brief Role Plays.** Participants will receive a vignette and prepare for a 45-60-minute role play, during which they will be asked to complete an SPI with a patient who was determined to be at-risk for suicide following CSSRS administration with a trained actor. Role plays will be audio-recorded and coded for competence with the Safety Planning Intervention Rating Scale (SPIRS). This will be administered at Time 3 and Time 4.

- An example of the procedures and coding scheme for the role play are included for the IRB's review.

Secondary Outcomes: Additional Mechanisms of Interest

- **Self-Perceived Knowledge & Attitudes About Suicide Scale.** Selected subscales (Knowledge, Attitudes) of the Short Survey on Knowledge, Self-Confidence, and Attitudes Towards Suicidal Behavior will assess a clinician's perceived knowledge about suicide and how to intervene. This will be administered at Time 1- 4.
 - This measure was previously reviewed and approved by the IRB.
- **Clinician Attitudes Toward Safety Planning.** A 12-item questionnaire assessing clinician attitudes and beliefs about the use of safety planning interventions in clinical practice with suicidal patients. This will be administered at Time 1- 4.
 - This measure was previously reviewed and approved by the IRB.
- **SSAI Intentions and Determinants of Intention.** Established question stems from behavioral science using items on a 7-point scale asking how willing and how likely one is to use SSAs as well as attitudes and perceived norms of SSAI use. This will be administered at Time 1- 4.

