Quantitative analyses This pilot feasibility trial is not intended to be adequately powered to detect significant effects.^{94,95} Findings will provide key preliminary data to support the feasibility of EBIS and study procedures for a fully powered R01 (e.g., frequency of suicidal ideation over the 8-week follow-up period). Qualitative analysis of interview transcripts and mixed methods analysis will supplement quantitative analyses.

Preliminary Analysis. Data screening and missing data analysis will be conducted in accordance with best practice recommendations.⁹⁶ Prior to conducting main analyses, we will examine the psychometric properties of all scales used to assess constructs of interest (e.g., coefficient alpha) to confirm adequate performance. We will conduct analyses of baseline variables as a randomization check to ensure comparable baseline characteristics for clinicians in EBIS and IAU. Any differences will be controlled for in subsequent analyses.

Hypothesis 1: EBIS will be an acceptable and feasible implementation strategy. We will calculate descriptive statistics on the AIM and FIM measures and compare scores between EBIS and IAU. We will also evaluate EBIS feasibility by calculating the proportion of clinicians randomized to EBIS who complete all exposure tasks.

Exploratory Hypotheses 1 and 2: EBIS will engage target implementation mechanisms of clinician anxiety and self-efficacy better than IAU; clinicians randomized to EBIS will show improved SSAI adoption and fidelity relative to clinicians randomized to IAU. We will examine the effect of condition over time on target mechanisms (anxiety and self-efficacy) and implementation outcomes (mean CSSRS screening frequency across encounters, proportions of appropriate encounters in which clinicians conduct follow-up assessment with the CSSRS and SPI use, as measured by CSR, and average SPI fidelity scores on role plays) using repeated measures analysis of covariance (ANCOVA), controlling for organization (given the small sample size and that we will recruit from only a small number of organizations for this pilot, we do not anticipate the need for multilevel analysis).

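### T1 scores become covariates only if a balance check with no stated criterion finds the arms different; always adjusting for them would narrow the exploratory intervals, and each outcome needs one named contrast

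*Combined protocol and SAP*

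**What the plan says.** Under Study Procedures, 5. Statistical Analysis, the Preliminary Analysis paragraph states: "We will conduct analyses of baseline variables as a randomization check to ensure comparable baseline characteristics for clinicians in EBIS and IAU". It continues: "Any differences will be controlled for in subsequent analyses". No test, threshold or list of variables is given for deciding that a difference exists.

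The paragraph on Exploratory Hypotheses 1 and 2 then states one target for all outcomes, "We will examine the effect of condition over time on target mechanisms (anxiety and self-efficacy) and implementation outcomes", to be analysed "using repeated measures analysis of covariance (ANCOVA), controlling for organization". It does not say whether T1 is a covariate or a level of time. It also does not say whether the result is a main effect of condition, an interaction or an arm difference at a given visit.

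Study Instruments and Table 2 put the outcomes on three schedules:

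- Anxiety and self-efficacy: T1, T2, T3 and T4.
- SSAI use by chart-stimulated recall (CSR): "This will be administered at Time 1 and 3-4".
- SPI fidelity by role play: T3 and T4 only. The analysis text describes this outcome as "average SPI fidelity scores on role plays".

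CSR reviews the clinician's "caseload with them for the past clinic week and ask them brief questions". Two of the CSR outcomes are "proportions of appropriate encounters in which clinicians conduct follow-up assessment with the CSSRS and SPI use", so they are undefined for a clinician who had no appropriate encounter in the week reviewed.

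**The concern.** T1 values are collected on every clinician for anxiety, self-efficacy and CSR screening. With 40 clinicians, a baseline measure of the outcome itself is the cheapest source of precision available. The plan uses it as a covariate only after an undefined check, so the covariate set depends on the data and on a criterion the analyst has still to choose.

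A single phrase for the target also has to cover outcomes with and without a T1 value. For fidelity, if the phrase is taken as condition-by-time, the test asks only whether the gap between arms changes from T3 to T4. A benefit of the same size at both visits then has an expected interaction of zero.

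At stake are the width of the intervals and the room left for choosing a contrast after the results are seen. The Background says the data will inform an R01, so the estimates and their intervals are worth getting right even though the pilot claims no power.

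**Working it through.** The documents give no power, SD, effect size or correlation, so there is no stated figure to reproduce.

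**Inputs from the documents.** 20 clinicians per arm; 3 to 5 organizations (four used here; three or five change the half-widths by about 0.002 SD at most); the visit schedules above.

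**Assumptions.** Outcome SD 1; the same correlation r between all visits, at 0.3, 0.5 and 0.7; no dropout; two-sided 95% intervals; the average of the k post-training visits as the outcome.

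**Per-clinician variance.**

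- Post-training mean, T1 unused: M = (1 + (k − 1)r)/k.
- Change from T1: M + 1 − 2r.
- T1 as covariate: M − r², times a small-sample factor 1 + 1/(df − 1).

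Before that factor, T1 adjustment has smaller variance than change by (1 − r)², and smaller than the unadjusted mean by r². It therefore cannot do worse than either, apart from the cost of estimating one slope.

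**Half-width** = t × √(2/20 × variance). Residual df are 40 − 1 − 4 = 35 without T1 and 34 with it; t = 2.03 in both cases. The factor is 1 + 1/33 = 1.03.

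Worked case, k = 3, r = 0.5:

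- M = (1 + 1)/3 = 0.667.
- Change: 0.667 + 1 − 1 = 0.667; half-width 2.03 × √0.0667 = 0.52.
- T1-adjusted: (0.667 − 0.25) × 1.03 = 0.429; half-width 2.03 × √0.0429 = 0.42.

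| 95% CI half-width (SD) | r = 0.3 | r = 0.5 | r = 0.7 |
|---|---|---|---|
| Anxiety, self-efficacy (k = 3): T1 unused | 0.47 | 0.52 | 0.57 |
| Change from T1 | 0.62 | 0.52 | 0.41 |
| T1 as covariate | 0.43 | 0.42 | 0.36 |
| CSR screening (k = 2, treated as continuous): T1 unused | 0.52 | 0.56 | 0.59 |
| Change from T1 | 0.66 | 0.56 | 0.43 |
| T1 as covariate | 0.49 | 0.46 | 0.39 |

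For k = 3 the variance ratio of change to T1-adjusted is 0.933/0.457 = 2.04, 0.667/0.429 = 1.55 and 0.400/0.319 = 1.25.

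**Adjusting only if different.** This belongs to the reading in which T1 is otherwise unused. If the check were a 5% test on the T1 score, it would flag only imbalances above 2.03 × √(2/20) = 0.64 SD, in about 5% of trials. The imbalance has SD √(2/20) = 0.316, so values between 0.3 and 0.64 SD arise in about 30% of trials and stay unadjusted. At r = 0.5 these shift a post-training comparison by 0.5 × 0.3 = 0.15 to 0.5 × 0.64 = 0.32 SD. In simulation with a single follow-up visit, the full CI width under the conditional rule was 1.33/1.33/1.32 SD, against 1.29/1.17/0.96 SD with T1 always included.

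**Cost of always adjusting.** If r = 0 the variance rises by about 3%. For a single follow-up visit, break-even is at r of about 0.17 to 0.18.

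**CSR follow-up proportions.** Suppose appropriate encounters in the T1 week are Poisson with mean 1 or 2 (an assumption). Then e⁻¹ = 37% or e⁻² = 14% of clinicians have no T1 value, leaving about 25 or 35 of 40. Dropping the others to adjust for T1 pays only if r exceeds √0.37 = 0.61 or √0.135 = 0.37.

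**SPI fidelity (T3, T4).** The T3/T4 mean has variance (1 + r)/2 and the interaction 2(1 − r). They are equal at r = 0.6. At r = 0.7 the half-widths are 0.59 SD for the mean and 0.50 SD for the interaction.

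**The case against.** The strongest reply is that a repeated measures analysis of condition over time, on outcomes measured from T1 to T4, most naturally carries T1 as a level of time. On that reading T1 is used for every clinician, and the change contrast already removes the T1 difference between arms. This stands. A reader might infer that T1 is ignored unless the arms differ; the documents support that only for T1 as a covariate. What remains is that change from T1 is still less precise than covariate adjustment at each correlation examined.

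A reader might also add the losses together. They belong to different analyses: uncorrected imbalance arises if T1 is left out, and the wider change interval arises if T1 is a repeated level. Nor does the plan set a 5% test. A 20% trigger would act at about 0.41 SD, so the 0.64 SD figure is only an illustration.

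For fidelity, the plan's wording about average scores and improvement relative to IAU fits a comparison of levels, so it cannot be said that the plan will test fidelity by interaction. Likewise, a condition main effect that averages T1 in with the later visits would dilute a sustained effect (to 3/4 for T1-T4 outcomes, 2/3 for CSR). That fits the text poorly and should not be charged to the plan.

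The post-training average is not the only defensible contrast. Consultation differs by arm and runs over 12 weeks, so an effect might appear mainly at T4, and averaging would dilute it. The choice belongs to the team.

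Finally, the pilot disclaims power, and nothing says these estimates will size the R01. That limits the severity but does not remove the reason to use data already collected.

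**Conclusion.** The point holds as a minor one. T1 is not an unconditional covariate, the trigger for using it as one has no criterion, and no contrast is fixed for any outcome. For anxiety, self-efficacy and CSR screening frequency, always including T1 gives narrower intervals than either reading the text allows. Against the change contrast on T1-T4 outcomes, the variance falls by a factor of about 2.04/1.55/1.25 at r = 0.3/0.5/0.7. These sizes rest on assumed equal correlations, 20 analysed per arm and no dropout; the documents supply none of the correlations.

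The precision claim does not extend to two places. For CSR follow-up proportions the gain is uncertain, because T1 may be undefined for many clinicians. For SPI fidelity there is no T1, and the T3/T4 mean is tighter than the interaction only if r is below 0.6. Naming a level difference there settles the estimand.

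The affected analyses are exploratory. The primary acceptability and feasibility results do not depend on this.

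**What to change.** State for each outcome the visits analysed, the role of T1 and one main contrast, all within the planned ANCOVA:

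- **Anxiety and self-efficacy:** T2-T4 as the repeated outcome, with the outcome's own T1 value and organization as covariates regardless of baseline balance.
- **CSR screening frequency:** the same, with T3-T4 as the outcome.
- **CSR follow-up proportions:** the same, plus a stated rule that keeps clinicians with no T1 value, for example a missing-T1 indicator.
- **SPI fidelity:** an arm difference in level, adjusted for organization, either averaged over T3 and T4 or at T4.
- **All outcomes:** choose the post-training average or T4 as the main contrast before the data are seen. Report arm differences by visit with 95% CIs, and keep condition-by-time as supplementary.

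The cost is wording in the analysis section and no new data: one degree of freedom for T1 (two for the CSR proportions), and about 3% in variance if T1 turns out to be unrelated to the outcome. Clinicians with no appropriate encounter at T3 or T4 remain a missing-outcome problem that this change does not solve.

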Aim 3: We will recruit clinicians for the pilot trial (n = 40) from 3-5 of our local partner community agencies with whom we have close relationships. Recruited agencies will be identified in collaboration with our Advisory Board and our partners within the City of Philadelphia Department of Behavioral Health. Clinics will be eligible if they have clinicians who provide direct mental health services to a mental health treatment-seeking population. We will only connect with clinicians working in these institutions if we receive clinic approval. We will not contact any clinicians if we do not have approval from clinic leadership or the clinician does not express interest in participating. To recruit clinicians, the study team will develop email scripts and flyers to disseminate to local agency partners who will in turn share these recruitment materials with their clinicians on staff. If it is preferred by the agency, the study team will collaborate with leadership in these agencies to identify a time for [name] or [name] or another senior member of the study team to attend a clinic team meeting (either virtually or in person) to present an overview of the study to interested clinicians. At this meeting, clinicians will complete a paper or electronic "consent to contact" via REDCap with their preferred contact information. Following the same procedures described in Aim 2 above, study staff will then follow up with interested clinicians to provide more information and to review all elements of informed consent.

Recruitment materials and scripts specific to the procedures in Aim 3 are included for the IRB's review.

5. Early Withdrawal of Subjects:

There is little risk associated with this study, and there is no safety concern associated with participation that would lead to participants being withdrawn from the study by the investigators. Importantly, exposure-based treatments upon which the EBIS implementation activities are based are generally well-tolerated with few, if any, side effects (see **Risks** below). As outlined in the informed consent document, there will be no consequences for any providers or other personnel who indicate interest and then do not enroll in the study. All participants will be free to withdraw their participation at any time by contacting study staff to inform them that they no longer wish to participate in the study.

6. Vulnerable Populations:

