SSAI Knowledge	Self-Perceived Knowledge About Suicide Scale ⁸³	X	X		X
SSAI Attitudes	Attitudes Toward Suicide Prevention; ⁸⁴ Clinician Attitudes Toward Safety	X	X	X	X

	Planning ⁸⁵				
SSAI Intentions	Established question stems ⁸¹		X	X	X X
SSAI Norms	Established question stems ⁸¹		X	X	X X
Demographics	Demographics survey		X		
Organizational Factors	Organizational Innovation Specific Capacity for Suicide Prevention Evidence-based practices (OISCSE)		X		
T1=baseline. T2=post-training. T3=2-week. T4=12-week follow-up.					

2. Group Modifications:

Aims 1 and 2: N/A

Aim 3: After consenting to participate, clinicians will be randomly assigned to one of the two implementation conditions; the measurement battery will be identical for clinicians in each condition, with the exception that qualitative interviews for clinicians randomized to the EBIS condition will include several additional questions about their specific experience with EBIS.

3. Method for Assigning Subjects to Groups:

Aim 1: N/A

Aim 2: No participants will be randomized as a part of Aim 2 activities.

Aim 3: Clinician participants will be randomized 1:1 to receive either Implementation as Usual (IAU) or IAU+EBIS. Randomization will take place after the informed consent process and prior to beginning either training condition.

4. Administration of Surveys and/or Process:

Aim 1: N/A

Aim 2: To accomplish Aim 2, we will deliver the draft version of EBIS as outlined in the procedures below. Following receipt of the draft version of EBIS, clinicians will complete brief 45-60 minute qualitative interviews with trained study staff. Qualitative interviews will take place via phone, videoconference, or in person, depending on participant preference.

Aim 3: During the clinical trial, all measures will be administered by trained research staff in accordance with the assessment schedule outlined above. Questionnaires at each time point will be administered either in paper format or electronically using REDCap, depending on participant preference (See *Study Instruments* above). Qualitative interviews will take place via phone, videoconference, or in person, depending on participant preference.

5. Data Management:

Drs. [name] (PI) and [name] (co-PI) will oversee all data cleaning and management with support from co-Investigator [name].

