In this prototyping phase, EBIS will be administered either individually to clinicians or in small groups of 2-4 clinicians. The syllabus that will guide EBIS administration is included for the IRB's review. All trainings and consultation sessions will be video recorded and transcribed using HIPAA compliant software. During administration, study staff will take field notes on implementation challenges. Clinicians will complete a brief demographic questionnaire before and after completing the training. After receiving EBIS, clinicians will complete brief qualitative interviews (45-60 minutes) about their experience with EBIS either virtually or at a private location (e.g., the University of Pennsylvania campus or your office location). Interviews will be audio-recorded and transcribed. The first part of the interview will query clinicians on acceptability and feasibility of EBIS. The second part will comprise semi-structured questions about perceptions of how EBIS influenced anxiety and self-efficacy to deliver the CSSRS and SPI. The last part will solicit suggestions for improvements to optimize EBIS. Clinicians will also receive continuing education credits for training activities. We anticipate it will take clinicians approximately 4-5 hours to complete study procedures (up to 4 hours of training and 1 hour for the interview).

We will make iterative refinements after each EBIS administration in response to observed implementation challenges and clinician feedback until saturation is reached (anticipated maximum: 20 clinicians). When clarity is needed on whether certain adaptations are needed, we will return to our Advisory Board for guidance.

The finalized manual that will guide EBIS administration in Aim 3 was submitted for the IRB's review.

Aim 3: Test acceptability, feasibility, and preliminary effectiveness of EBIS to target implementation mechanisms and outcomes relative to implementation as usual (IAU) via a pilot randomized trial.

After consenting, clinicians will be randomized to one of two implementation arms: IAU (n=20), or EBIS (n=20), which comprises all IAU activities plus EBIS as refined in Aim 2. If a clinician drops out of the study prior to attending their initial workshop (which is when official randomization will occur), we will make efforts to replace that individual to obtain a final sample of 40 clinicians randomized.

IAU Condition. Gold-standard IAU for SSAs typically comprises pre-implementation

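### Repeated measures ANCOVA is named for the exploratory outcomes with no missing-data method; in its standard form it drops clinicians with any missed visit, which wastes data and can bias the EBIS-IAU contrast in either direction

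*Combined protocol and SAP*

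**What the plan says.** Under STUDY PROCEDURES, 5. Statistical Analysis, Exploratory Hypotheses 1 and 2, one model serves the mechanisms (anxiety, self-efficacy) and the implementation outcomes (CSSRS screening, follow-up assessment and SPI use from chart-stimulated recall, and role-play fidelity). The effect of condition over time is to be examined "using repeated measures analysis of covariance (ANCOVA), controlling for organization". The same sentence adds that "we do not anticipate the need for multilevel analysis", because the sample is small and the organizations are few.

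The only text on missing data is under Preliminary Analysis: "Data screening and missing data analysis will be conducted in accordance with best practice recommendations". It cites an outside source and names no method. No analysis set and no expected dropout rate are given.

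Two other sections decide where gaps can arise. Early Withdrawal of Subjects states: "All participants will be free to withdraw their participation at any time by contacting study staff". The Aim 3 procedures provide for replacement only in one case: "If a clinician drops out of the study prior to attending their initial workshop". Later losses are not replaced.

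By Table 2, anxiety and self-efficacy are measured at T1 to T4, chart-stimulated recall at T1, T3 and T4, and role plays at T3 and T4.

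**The concern.** Repeated measures ANCOVA, as commonly fitted, needs a complete row for each clinician. A clinician who gives T1, T2 and T3 and then leaves would drop out of the anxiety and self-efficacy analyses altogether. The same holds for chart-stimulated recall: leaving before T3 loses the T1 value, and leaving before T4 loses T1 and T3. For fidelity, a missed role play discards the one score that was collected. Leaving before T3 discards no role play, since none has taken place.

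With 20 clinicians per arm, each one dropped is 5% of an arm. The contrast would then rest on those who stayed throughout. If the reasons for leaving are tied to anxiety in one arm and not in the other, the remaining groups are no longer comparable.

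**Working it through.** **Inputs from the documents.** 40 clinicians, allocated 1:1 (20 per arm). Visits as in Table 2. T2 is immediately after training. The plan gives no dropout rate, correlation, effect size or standard deviation, so it has no figure of its own to reproduce.

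**Assumptions.** The dropout rates, a correlation of 0.6 between visits, SD 1 and a true effect of -0.50 SD at T2 to T4 are all assumed.

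**1. Complete rows.** T2 follows directly on training, so loss there should be near nil and only T3 and T4 are counted. With a share m missing independently at each, complete rows = 40 × (1 − m)²:
- m = 0.05: 40 × 0.9025 = 36.1
- m = 0.10: 40 × 0.81 = 32.4
- m = 0.15: 40 × 0.7225 = 28.9

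**2. Observations discarded.** Suppose total dropout is D, half before T3 and half before T4. For anxiety and self-efficacy, an early leaver has one post-baseline value (T2) and a late leaver has two (T2, T3).
- D = 10%: 2 × 1 + 2 × 2 = 6 discarded, of 36 × 3 + 6 = 114 collected (5%)
- D = 20%: 4 × 1 + 4 × 2 = 12, of 32 × 3 + 12 = 108 (11%)
- D = 30%: 6 × 1 + 6 × 2 = 18, of 28 × 3 + 18 = 102 (18%)

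For role plays, only late leavers lose a collected score: 2 of 74, 4 of 68 and 6 of 62.

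**3. Precision.** In 1,000 simulated trials of 40 clinicians with 20% completely random dropout, the standard error of the contrast averaged over T2 to T4 was 0.226 SD for complete-row ANCOVA (T1 as covariate). It was 0.209 for a likelihood fit to all observed visits. The ratio is 0.226 / 0.209 = 1.08.

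**4. Bias.** From large simulated samples (100,000 clinicians), for the same averaged contrast:

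| Dropout mechanism | Complete rows, bias at 10 / 20 / 30% | Likelihood, bias |
|---|---|---|
| Completely random | about 0 | about 0 |
| Depends on T2 score, same in both arms | about 0 | about 0 |
| Depends on T2 score, EBIS only (high anxiety leaves) | -0.05 / -0.09 / -0.12 SD | about 0 |

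The T2 contrast is hit hardest: at 20% EBIS dropout it is -0.65 against -0.50, although T2 was observed for everyone. If low-anxiety EBIS clinicians leave instead, the simulated distributions are mirrored and the bias has the same size with the opposite sign, so EBIS looks worse than it is.

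**5. Bias against noise at n = 40.** With 20% EBIS-only dropout, the three complete-row contrasts average (-0.654 − 0.557 − 0.546) / 3 = -0.586, a bias of -0.086, with spread 0.199. Root mean square error = √(0.086² + 0.199²) = 0.217. The likelihood fit averages -0.500 with spread 0.191, so its root mean square error is 0.191.

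**The case against.** The strongest objection is that the plan never says listwise deletion. Repeated measures ANCOVA names a type of analysis, and the deletion comes from the usual way of fitting it. The best-practice sentence is not confined to data screening and could cover multiple imputation, after which nothing would be discarded. This stands in part: a reader might infer that the plan ignores missing data or has chosen to discard it, and the text does not support that. What remains is that no method that keeps partial data is named, so the choice could be made after the data are seen.

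A second objection is that the bias depends on an assumed mechanism. That is right. The documents give no evidence of dropout that differs by arm. It is plausible because exposure work is given only in EBIS, but no more than that. A reader might infer that EBIS will look better than it is; the direction depends on who leaves.

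Third, retention is actively supported. Subject Follow-up describes payment after each assessment and scheduling outside business hours, and the largest payment is at T4. Dropout may therefore be at the low end of the range.

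Fourth, a reader might infer that a future R01 will be sized on these estimates. The Statistical Analysis section ties the findings to the feasibility of EBIS and of study procedures, and does not say that.

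Finally, the remark against multilevel analysis might seem to rule out a mixed model. Its stated reasons concern clustering within organizations. A model with clinician as the repeated unit and organization as a fixed effect is consistent with it.

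**Conclusion.** The point holds in a limited form. The named model, in its standard form, would drop clinicians with a missed visit, and the plan names nothing that prevents this. At an assumed 10 to 30% dropout, 5 to 18% of collected post-baseline anxiety and self-efficacy values would be unused. The standard error would be about 8% larger at 20% random dropout. Bias of about 0.05 to 0.12 SD on a true 0.50 SD appears only when leaving depends on scores in one arm and not the other, and it can go either way. It is smaller than the sampling error of about 0.2 SD at n = 40.

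Severity is moderate. The outcomes are exploratory, the pilot is declared not to be adequately powered, and the primary acceptability and feasibility outcomes do not use this model.

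**What to change.** For outcomes measured repeatedly, replace repeated measures ANCOVA with a likelihood-based mixed model for repeated measures. Use arm, visit, arm-by-visit and organization as fixed effects, clinician as the repeated unit, an unstructured covariance with a simpler fallback stated in advance, and small-sample degrees of freedom. Fit it to every observed visit of all randomized clinicians. Alternatively, keep the ANCOVA and state that it follows multiple imputation. In either case, report the number of clinicians contributing at each visit by arm.

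The cost is a sentence in the analysis section and standard software; no new data are needed. There are two drawbacks. The covariance may have to be simplified with 40 clinicians. The model also corrects only for dropout explained by observed scores. In a separate simulation (20 per arm, correlation 0.6, about 32 to 33 complete, true effect -0.50), when leaving depended on the unobserved T4 score the likelihood estimate was also biased, at about -0.64, against -0.75 for complete rows.
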